#### **15.3.4.1. Efficacy Analyses**

In general, continuous data will be summarized using descriptive statistics, and categorical data will be summarized using counts and percentages, as described above in Section [15.3.3.6](#). Specific analysis details and display format will be described in the statistical analysis plan.

##### **15.3.4.1.1. Analyses of Ambulatory Function and Pulmonary Function**

Efficacy variables (6MWD [m]), percent predicted 6MWD, and percent predicted sitting FVC) will be summarized over time for the assessment visits that occurred post-DBL of the final CSR, based on the OLE-RS population. Where a change from baseline summary is required, the baseline result will be based on the last assessment prior to the DBL of the final CSR. A 95% confidence interval for the mean change from baseline will be provided where applicable. For the analysis of percent predicted 6MWD, the predicted value will be calculated using the reference equations from Enright and Sherill ([Enright and Sherill 1998](#)).

#### **15.3.4.2. Safety Analyses**

Safety data will be summarized on the OLE-RS population. Visit-based safety variables will be summarized over time for the assessment visits that occurred post-DBL of the final CSR. Where change from baseline or percent change from baseline summaries are required, the baseline results will be based on the last assessment made prior to the DBL of the final CSR.

Safety data will be summarized using descriptive statistics for continuous data and using counts and percentages for categorical data, as described in Section [15.3.3.6](#).

Exposure to study medication will be calculated in weeks and analyzed as continuous variables using descriptive statistics. In addition, the duration of exposure will be categorized and a frequency distribution of the categories (each summarized by count and percentage) will be presented.

An overall summary of incidence of AEs (which includes the total number of TEAEs, total number of serious TEAEs as well as the total number of subjects) will be presented. The number and percentage of subjects who experienced nonserious TEAEs as well as serious TEAEs will be summarized by preferred term within system organ class. The summary of nonserious and serious TEAEs will also be presented by intensity (mild, moderate, severe), as well as by relationship to study medication. In addition, the number of AEs (as opposed to the number and percentage of subjects) will be presented.

Serious adverse events, including deaths, will be summarized and listed. Separate listings of death, SAEs (treatment-emergent and nontreatment-emergent), and discontinuations due to AEs will be provided.

Summaries and listings will also be provided for deaths, SAEs, and AEs leading to discontinuation and infusion-associated reactions. Adverse events will be coded using Medical Dictionary for Regulatory Activities version 18 or higher.

Clinical laboratory results, ECG parameters, and vital signs will be summarized using descriptive statistics (number, mean, median, standard deviation, minimum, and maximum) by treatment group and visit for actual values and changes from baseline. The proportion of subjects with abnormalities will be provided for clinical laboratory results, ECGs, and vital signs. Shift tables will also be provided for clinical laboratory results.

Concomitant medications and nondrug therapies will be summarized by treatment group. Concomitant medications terms will be coded using the World Health Organization Drug Dictionary (September 2013 DDE).

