### 12.3.10. Electrocardiogram

A standard 12-lead ECG will be performed after subjects have rested for approximately 5 minutes prior to the start of the ECG recording. Subjects will be in the supine position throughout the ECG evaluation. A central ECG vendor will be used.

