### 12.3.11. Clinical Laboratory Tests

#### 12.3.11.1. Chemistry, Hematology, and Urinalysis

Clinical laboratory tests for safety monitoring include serum chemistry (Table 6), hematology (Table 7), and urinalysis (Table 8). Clinical laboratory tests will be performed prior to administration of study drug. The collection, processing, and shipment of all biological samples will be fully described in the study laboratory manual.

The investigator (or his/her designee) will review each laboratory report from the central laboratory and assess any out-of-range laboratory results as "not clinically significant" or "clinically significant" (see Appendix 3). Any results that are considered clinically significant should be confirmed in a repeat test at the investigator's discretion. The investigator should consider repeat testing of persistent clinically significant results until the analyte returns to normal or until an etiology is determined. The investigator (or his/her designee) will sign and date all laboratory reports. Results for CK, alanine aminotransferase (ALT), and aspartate aminotransferase (AST) will be blinded to investigators and reviewed by an unblinded medical monitor until treatment assignments in Study ATB200-03 are unblinded to maintain consistency.

After approval of this amendment, clinical laboratory tests will be performed locally at site.

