**Table 10: Schedule of Assessments for Subjects Who Continue Under Protocol Amendment 3 (Continued)**

Study Visit	Treatment			Follow-up ≥ 30 Days After Last Dose
	Infusion Visits (Every 2 Weeks Through EOS/ET)	Every 52 Weeksa	EOS/ET	
Visit Window (Days)	± 3	± 3	± 3	± 3
Study Drug Administration				
Miglustat (10)	Every 2 weeks 1 hour before infusion of cipaglucosidase alfa			
Cipaglucosidase alfa (10)	Every 2 weeks			

Abbreviations: 6MWT = 6-minute walk test; AE = adverse event; ECG = electrocardiogram; EOS = end of study; ET = early termination; FVC = forced vital capacity; IRT = interactive response technology; PE = physical examination; SAE = serious adverse event

a Study visits will be scheduled every 52 weeks until study termination by the sponsor.

b Complete physical examinations will include assessment of head, ears, eyes, nose, throat (HEENT), respiratory, cardiovascular, lymphatic, gastrointestinal, and neurologic systems.

c Weight will be entered into the IRT system every 52 weeks for calculation of cipaglucosidase alfa dose.

d Test to be performed locally.

e Urine pregnancy tests are performed locally only for female subjects of childbearing potential. If the urine pregnancy test has a positive result, study drug will not be administered and a confirmatory serum pregnancy test will be performed.

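### Amendment 3 moves chemistry and hematology to local laboratories, but Appendix 1 still summarises raw change from a baseline that may be a central result, so laboratory differences can appear as change over time or mask it

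*Protocol*

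**What the plan says.** Before Amendment 3 the laboratory source is central: under Protocol 12.3.11.1 the investigator or designee "will review each laboratory report from the central laboratory". The same section ends with the new rule: "After approval of this amendment, clinical laboratory tests will be performed locally at site". In Table 10, the schedule for subjects who continue, footnote d is attached to the serum chemistry and hematology row and to the 12-lead ECG row, and reads "Test to be performed locally".

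Appendix 1, 15.3.4.2, plans that "Clinical laboratory results, ECG parameters, and vital signs will be summarized using descriptive statistics", presented "by treatment group and visit for actual values and changes from baseline". Where change is needed, "the baseline results will be based on the last assessment made prior to the DBL of the final CSR". The section also plans the proportion of subjects with abnormalities, and it adds: "Shift tables will also be provided for clinical laboratory results".

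Appendix 1, 15.3.2, defines one treatment group, and Table 10 sets assessment visits every 52 weeks. Appendix 1, 15.3.4, leaves analysis detail to the statistical analysis plan. The SAP supplied limits itself, in its Introduction, to the final CSR at the 31 December 2024 cutoff.

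**The concern.** The laboratory and ECG paragraph of Appendix 1, 15.3.4.2, is the same as that in main-body section 15.3.4.4, which was written for central measurement. The source of the laboratory values changed and the analysis did not. For a subject whose last pre-DBL result is central, every change from baseline is a local value minus a central value. Any difference in assay or calibration enters at the same moment as follow-up begins. There is no comparator in which the same switch occurs without the passage of time.

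Long-term safety is the primary objective, and Amendment 3 exists partly to extend that record. Appendix 3 notes that AST, ALT and LDH are known to be elevated in some adults with Pompe disease and judges such analytes partly against the subject's baseline. These are values for which a shift at the switch could be read as a liver or muscle signal, or could cancel a real one.

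**Working it through.** The plan gives no figure to reproduce: there is no offset, SD of change, DBL date or number of continuing subjects. The check compares the passages first and then illustrates the effect on assumed inputs.

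**1. Passages side by side**

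| Item | Up to Amendment 3 | Under Amendment 3 |
|---|---|---|
| Chemistry, hematology | Central laboratory (12.3.11.1) | Local (12.3.11.1; Table 10, footnote d) |
| Summary | Actual values and change by visit (15.3.4.4) | Same text (Appendix 1, 15.3.4.2) |
| Baseline | Last visit of Study ATB200-03, or Baseline Visit (12.2.1) | Last assessment before the DBL (Appendix 1, 15.3.4.2) |
| Rule for the change of laboratory | Not needed | None in the documents |

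**2. What the change score contains**

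Let *b* be the local-minus-central offset.

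- Central baseline: observed change = true change + *b*.
- Local baseline, same laboratory: observed change = true change.
- Second local value minus first local value, same laboratory: the offset cancels.

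If *b* is common to all sites and a share *s* of subjects has a central baseline, mean observed change = mean true change + *s* × *b*. More subjects do not reduce the last term. If offsets vary by site and average to zero, the effect is mainly added spread.

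**3. How many baselines are central**

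Local testing starts at amendment approval, but the baseline cut is the DBL. Assume evenly spread 52-week visits and a gap of *L* weeks from approval to DBL. Then *s* = 1 − *L*/52.

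- *L* = 0: 100%
- *L* = 4: 1 − 4/52 = 92%
- *L* = 13: 75%
- *L* = 26: 50%

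**4. How misleading a raw mean change could be**

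Take a true change of zero and *b* in units of the SD of change, so SE = 1/√n. The chance that a 95% interval excludes zero is 1 − Φ(1.96 − *s·b*·√n) + Φ(−1.96 − *s·b*·√n). For example, with *b* = 0.2, *s* = 1 and n = 100, *s·b*·√n = 2, and the chance is 1 − Φ(−0.04) + Φ(−3.96) = 52%.

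| Assumed offset | Central share | n = 20 | n = 50 | n = 100 |
|---|---|---|---|---|
| 0.2 SD | 100% | 15% | 29% | 52% |
| 0.2 SD | 50% | 7% | 11% | 17% |
| 0.5 SD | 100% | 61% | 94% | above 99% |

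The interval is only a yardstick here. The laboratory paragraph itself lists number, mean, median, SD, minimum and maximum.

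**5. Why scaling to ULN is not a complete answer**

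Assume a central ULN of 40 U/L for ALT and a local ULN of 0.8 to 1.3 times that, so 32 to 52 U/L. None of these figures is in the documents.

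- *If the ULN difference is all calibration*: a subject steady at 2 × ULN moves from 80 U/L to 2 × 32 = 64 (−16 U/L, −20%) or 2 × 52 = 104 (+24 U/L, +30%). Raw change misleads and the multiple of ULN does not.
- *If only the quoted range differs*: a subject steady at 80 U/L moves from 2.0 × ULN to 80/52 = 1.54 (−23%) or 80/32 = 2.5 (+25%). Now the multiple misleads and raw change does not. A steady 125 U/L goes from 125/40 = 3.1 to 125/52 = 2.4 × ULN and drops below a 3 × ULN threshold.

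Neither scale is safe alone across the switch. Change within one laboratory avoids both problems.

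**The case against.** The strongest reply is that much of the protection is already planned. Section 15.3.4.2 of Appendix 1 includes abnormality proportions and laboratory shift tables, and Appendix 3 sets its AST, ALT, alkaline phosphatase and LDH criteria as multiples of ULN. Investigators also judge out-of-range results one by one (12.3.11.1), and clinically significant ones are adverse events (13.1.1). The addendum is descriptive, tests no hypotheses, and may have its own SAP; local ranges may be handled in the Data Management Plan. Neither of those documents is among those supplied.

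Most of this stands, and it limits the harm: safety signals do not rest on mean change alone. It does not remove the point. Appendix 1 does not say whose reference range the shift tables and proportions use, and the raw-change tables remain a stated rule rather than an open detail.

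A reader might also infer that source is fully confounded with time throughout follow-up. The documents do not support that. The switch is a single step, later values from the same local laboratory share a source, and subjects whose last pre-DBL test was local have a local baseline. Nor does it follow that raw-unit change should be dropped outright: the second case in the working shows that ULN scaling can create an artefact of its own.

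**Conclusion.** The point holds for chemistry and hematology. Under the plan as written, subjects with a central baseline will have change scores that cross a change of laboratory, and nothing supplied tells the reader so or adjusts for it. Laboratory differences can therefore appear as change over time or mask it.

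The documents do not show that they will, or by how much. The percentages in the working depend on an assumed common offset, and the ALT figures on assumed reference limits. The share of subjects affected depends on the approval and DBL dates, which are not given.

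A reader might extend the point to ECG. The text does not settle that. Section 12.3.10 still states "A central ECG vendor will be used", and Table 10 cites that section while its footnote d says local. Performed locally could mean recorded at the site and still read centrally. This is a contradiction to reconcile, not an established change of method. Vital signs, named in the same sentence of Appendix 1, are not affected.

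**What to change.** In Appendix 1, 15.3.4.2, and in the addendum's statistical analysis plan:

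1. Record the source, units and reference range with each local laboratory result.
2. Base the planned shift tables and abnormality proportions on the range of the laboratory that reported each value, and make them the main laboratory display. Also show values and change as multiples of that laboratory's ULN or LLN where applicable.
3. Label any raw-unit change that crosses from central to local, and do not use it alone to infer change. Add change among same-source pairs, for example from the first local value.
4. For ECG, reconcile 12.3.10 with Table 10, footnote d, and state whether reading is central or local. Apply the same source labelling only if reading becomes local.

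The cost is some extra data entry and extra tables. Same-source change has fewer visits, since with 52-week spacing a subject who starts from the first local value gives up that visit as follow-up. ULN scaling reduces laboratory differences without removing them. Ranges are easiest to collect with each result, so the wording is best settled before local results accumulate.

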## **16. STUDY CONDUCT CONSIDERATIONS**

Please refer to Section 16 in the main body of the protocol.

## APPENDIX 2. SAMPSON CRITERIA FOR ANAPHYLAXIS

---

**Anaphylaxis is highly likely when any one of the following 3 criteria are fulfilled:**

---

1. Acute onset of an illness (minutes to several hours) with involvement of the skin, mucosal tissue, or both (eg, generalized hives, pruritus or flushing, swollen lips-tongue-uvula)  
*AND AT LEAST ONE OF THE FOLLOWING*
  - a. Respiratory compromise (eg, dyspnea, wheeze-bronchospasm, stridor, reduced PEF, hypoxemia)
  - b. Reduced BP or associated symptoms of end-organ dysfunction (eg, hypotonia [collapse], syncope, incontinence)
2. Two or more of the following that occur rapidly after exposure to a *likely allergen for that patient* (minutes to several hours):
  - a. Involvement of the skin-mucosal tissue (eg, generalized hives, itch-flush, swollen lips-tongue-uvula)
  - b. Respiratory compromise (eg, dyspnea, wheeze-bronchospasm, stridor, reduced PEF, hypoxemia)
  - c. Reduced BP or associated symptoms (eg, hypotonia [collapse], syncope, incontinence)
  - d. Persistent gastrointestinal symptoms (eg, crampy abdominal pain, vomiting)
3. Reduced BP after exposure to *known allergen for that patient* (minutes to several hours):
  - a. Infants and children: low systolic BP (age specific) or greater than 30% decrease in systolic BP\*
  - b. Adults: systolic BP of less than 90 mm Hg or greater than 30% decrease from that person's baseline

---

*PEF*, Peak expiratory flow; *BP*, blood pressure.

\*Low systolic blood pressure for children is defined as less than 70 mm Hg from 1 month to 1 year, less than (70 mm Hg + [2 × age]) from 1 to 10 years, and less than 90 mm Hg from 11 to 17 years.

Source: [Sampson, Muñoz-Furlong et al. 2006](#)

### **APPENDIX 3. POTENTIALLY CLINICALLY SIGNIFICANT GUIDELINES**

Criteria for identifying abnormalities as potentially clinically significant are based on the Guidelines for the Division of Neuropharmacological Drug Products, US Food and Drug Administration (revised on 2 April 1987). The laboratory values identified below are not inclusive of all the safety laboratory analytes that will be assessed during this clinical trial. Safety laboratory analytes that are known to be elevated in some adults with Pompe disease (eg, aspartate aminotransferase, alanine aminotransferase, lactate dehydrogenase) and safety laboratory analytes which are not listed below will be reviewed to determine if they are to be noted as potentially clinically significant based on the magnitude of the out of range value as compared with the normal range and the subject's baseline value, and whether the out of range value is coded as clinically significant by the principal investigator.

Laboratory Values		
Variable	Criterion Values	
	Standard Units	SI Units
Chemistry		
SGOT (AST)	$\geq 3 \times$ Upper Limit Normal	
SGPT (ALT)	$\geq 3 \times$ Upper Limit Normal	
Alkaline Phosphatase	$\geq 3 \times$ Upper Limit Normal	
LDH	$\geq 3 \times$ Upper Limit Normal	
BUN	$\geq 30$ mg/dL	$\geq 10.7$ $\mu$ M
Creatinine	$\geq 2.0$ mg/dL	$\geq 176.8$ $\mu$ M
Uric Acid	Male Female	$\geq 10.5$ mg/dL $\geq 8.5$ mg/dL
Bilirubin (Total)		$\geq 34.2$ $\mu$ M
Hematology		
Hematocrit	Male Female	$\leq 37\%$ $\leq 32\%$
Hemoglobin	Male Female	$\leq 11.5$ g/dL $\leq 9.5$ g/dL
Platelets		$\leq 75,000/\text{mm}^3$ or $\geq 700,000/\text{mm}^3$
Leukocytes		$\leq 2,800/\text{mm}^3$ or $\geq 16,000/\text{mm}^3$
Eosinophils		$\geq 10\%$
Neutrophils		$\leq 15\%$
Urinalysis		
Protein	Increase of $\geq 2$ units	
Glucose	Increase of $\geq 2$ units	
Casts	Increase of $\geq 2$ units	

Abbreviations: BUN = blood urea nitrogen; LDH = lactate dehydrogenase; SGOT (AST) = serum glutamic oxaloacetic transaminase (aspartate aminotransferase); SGPT (ALT) = serum glutamic pyruvic transaminase (alanine aminotransferase)

Vital Sign Values			
Variable	Criteria		Change Relative to Baseline
Heart Rate	$\geq 120$ bpm	and an	increase of $\geq 15$ bpm
	$\leq 50$ bpm	and a	decrease of $\geq 15$ bpm
Systolic Blood Pressure	$\geq 180$ mmHg	and an	increase of $\geq 20$ mmHg
	$\leq 90$ mmHg	and a	decrease of $\geq 20$ mmHg
Diastolic Blood Pressure	$\geq 105$ mmHg	and an	increase of $\geq 15$ mmHg
	$\leq 50$ mmHg	and a	decrease of $\geq 15$ mmHg
Weight			change of $\geq 7\%$ body weight

ECG Values		
ECG Parameter	Low	High
PR interval (ms)	$< 120$ ms	$\geq 210$ ms
QRS duration (ms)	$\leq 50$ ms	$> 120$ ms
QTcB interval (ms)	Not applicable	$> 450$ ms for males and $> 470$ ms for females and QTcB increases from baseline $> 60$ ms (males and females)
Ventricular rate (bpm)	A decrease from reference a $\geq 15$ bpm, and an absolute value $< 50$ bpm	An increase from reference a $\geq 15$ bpm, and an absolute value $> 120$ bpm

Abbreviations: ECG = electrocardiogram; QTcB = QT interval for corrected heart rate

a Reference value: baseline or initial visit value, as appropriate

## LIST OF ABBREVIATIONS AND DEFINITION OF TERMS

**Table 1: List of Abbreviations**

| Abbreviation | Term   |
|--------------|--|
| 6MWD         | 6-minute walk distance                                   |
| 6MWT         | 6-minute walk test                                       |
| AE           | adverse event  |
| CI           | confidence interval                                      |
| CK           | creatine kinase  |
| CSR          | clinical study report                                    |
| ECG          | electrocardiogram  |
| ERT          | enzyme replacement therapy                               |
| FAS          | full analysis set  |
| FVC          | forced vital capacity                                    |
| GSGC         | Gait, Stairs, Gowers' maneuver, and Chair test           |
| Hex4         | hexose tetrasaccharide                                   |
| IAR          | infusion-associated reaction                             |
| MMT          | manual muscle test                                       |
| OLE          | open-label extension                                     |
| OLE-ES       | open-label extension enrolled subjects                   |
| PD           | pharmacodynamic(s)                                       |
| PDLC         | pre-defined limits of change                             |
| PROMIS       | Patient-reported Outcomes Measurement Information System |
| PT           | preferred term   |
| QMT          | quantitative muscle test                                 |
| SAE          | serious adverse event                                    |
| SAP          | statistical analysis plan                                |
| SD           | standard deviation                                       |
| SE           | standard error   |
| SOC          | system organ class                                       |
| TEAE         | treatment-emergent adverse event                         |
| TESAE        | treatment-emergent serious adverse event                 |

## 1. INTRODUCTION

This statistical analysis plan (SAP) describes the planned data analyses and the outputs to be included in the final clinical study report (CSR) for the standalone open-label extension (OLE) Study ATB200-07. The SAP is based on Amendment 3 of the Protocol for Study ATB200-07 dated 10 December 2024.

This final SAP describes the analyses that will be performed for the final CSR for the standalone Study ATB200-07 based on a data cutoff date of 31 December 2024. All data collected through the cutoff date will be reported as summary tables and/or listings.

This SAP has been developed in accordance with Good Clinical Practice (GCP), International Council on Harmonisation (ICH) guideline E9 (Statistical Principles for Clinical Trials), and Amicus standard operating procedure (SOP) ATCRA-SOP-AT-008.

The analyses and statistical methods specified in the final SAP supersede those described in the study protocol.

## **2. STUDY OBJECTIVES**

### **2.1. Primary Objective**

The primary objective of this study is to assess the long-term safety and tolerability of ATB200/AT2221 combination treatment.

### **2.2. Secondary Objectives**

The secondary objectives of this study are as follows:

- to assess the long-term efficacy of ATB200/AT2221 combination on ambulatory function, as measured by the 6-minute walk test (6MWT)
- to assess the long-term efficacy of ATB200/AT2221 combination on pulmonary function, as measured by sitting forced vital capacity (FVC) (% predicted)
- to assess the long-term efficacy of ATB200/AT2221 combination on muscle strength
- to assess the long-term efficacy of ATB200/AT2221 combination on health-related patient-reported outcomes
- to assess the long-term efficacy of ATB200/AT2221 combination on motor function
- to assess the long-term efficacy of ATB200/AT2221 combination on overall clinical impression, as assessed by both physician and subject
- to assess the long-term efficacy of ATB200/AT2221 combination on measures of pulmonary function other than FVC (% predicted)
- to assess the long-term effect of ATB200/AT2221 combination on biomarkers of muscle injury and disease substrate
- to assess the immunogenicity of ATB200/AT2221 combination
- to characterize the pharmacokinetics of ATB200 and AT2221 using plasma total GAA protein level by signature peptide and plasma AT2221 concentration assays in subjects at sites in Japan only

